Individuals with Parkinson's disease (PD) experience difficulty participating in meaningful activities in their homes and communities due to slowing and increased energy expenditure of walking. Exercise that involves repetitive practice of stepping like treadmill walking, tango dancing or use of external cueing to facilitate larger steps improve walking performance in the PD population.¹⁻³ However, many individuals have difficulty adhering to regular exercise due to barriers including lack of access to exercise facilities, physical, cognitive, and psychologic (i.e., depression) impairments, and lack of motivation and/or self-efficacy.⁴ To promote optimal functional recovery, rehabilitation interventions that encourage neuroplastic changes must provide high repetition, task-oriented movement training that promotes learning and sensory input.⁵ Robotic devices have incited high interest among researchers and clinicians in the neurorehabilitation field because they can deliver high repetition task-specific training, while reducing the manual labor burden on therapists during delivery of the rehabilitation.⁶ Clinical trials of robot-assisted treadmill training in individuals with PD demonstrate significant improvements in functional mobility, gait speed, walking endurance, freezing of gait, and quality of life.⁷⁻¹¹ While these studies showed that people with PD accept and benefit from the use of robots, the robots used in these studies were large, heavy, complex robots (i.e., Lokomat, G-EO) that are cost prohibitive for most people and require months of training before they can be used independently. Recently, Honda Research and Development (R&D) developed a robotic exoskeleton called the Honda Walking Assist device (Honda R&D Co. Ltd., Wako, Japan) that is lightweight and portable with a goal of affordability and ease of use for therapists and patients.¹² The HWA facilitates walking in people with gait deficits with little robotic interference while providing repetitive training of a symmetrical gait pattern in the home environment (Figure 1). The device is worn around the user's waist and thighs, and assists with hip flexion during swing initiation and hip extension during stance. The robot automatically calibrates leg movements to spatial and temporal cadence targets.¹³ The device does not interfere with sitting and is not active during sit to/from stand transfers. Variable device settings allow for personalized, specific assistance. Advantages of wearable robotics such as the HWA include easy donning and doffing, and greater ease of use and free movement in the home and community, all of which

yield greater walking practice.¹⁴ **By allowing high repetition task-based exercise in the home and community, the use of the HWA has the potential to overcome exercise/activity barriers, thereby leading to improved gait parameters to prevent or slow functional decline and improve quality of life in individuals with PD.** Previous laboratory-based studies have examined the effects of HWA device usage on gait spatiotemporal parameters and efficiency in healthy adult and neurological populations.¹⁴⁻¹⁸ Healthy elderly and middle-aged adults showed temporary improvements in stride length, gait speed, and energy costs wearing the HWA compared to unassisted walking.^{15,16} Long-term HWA usage in patients with stroke improved gait parameters during unassisted walking.^{14,17} Preliminary findings in 12

[figure not shown]

Figure 1. Honda Walking Assist Device

individuals with PD showed improved gait speed and walking endurance during unassisted walking after 10-12 sessions of HWA training in a clinic.¹⁸ These preliminary findings of gait improvements in PD with HWA training warrant further study within home and community environments, and within a larger population of individuals with PD. Importantly, HWA training may be a useful intervention to overcome exercise barriers and improve mobility for daily life and warrants an innovative Phase II randomized controlled trial of real-world use over an extended period of time.

Project Objectives. This study will determine the impact of HWA usage on mobility in the home and community in individuals with PD. It will also examine feasibility and safety of HWA usage in the PD population. **As mobility limitations are highly associated with poor quality of life in people with PD,¹⁹⁻²¹ any benefits of HWA usage to improve mobility are likely to positively impact the health and well-being of individuals with PD.** **Specific Aim 1:** Determine the short-term impact of mechanical gait assistance on efficiency and ease of walking in individuals with PD. With disease progression, individuals with PD develop gait impairments (e.g., slower gait velocity, shorter step lengths, increased step-to-step variability, and freezing of gait), that interfere with their abilities to perform daily living tasks and participate in work, home, and social activities and predispose them to falls.²² *We hypothesize that wearing the HWA device will improve gait efficiency, gait parameters, and perceived ease of walking in individuals with PD compared to unassisted walking over a one session period.* Positive findings of immediate improved walking efficiency and perceived ease of walking will suggest that HWA usage can ameliorate gait impairments in individuals with PD, and thereby possibly allow them to more easily perform daily tasks, participate in work, home, and social activities, and reduce their fall risk. **Specific Aim 2:** Determine the effect of long-term HWA device usage on the ease and ability to walk unassisted in the home and community in individuals with PD. Angular sensors embedded in the HWA monitor the cadence, angular velocity, and degree of hip extension and flexion of the device user.¹⁴ When the user initiates walking, the HWA automatically adjusts leg movements to reach target walk ratios (step length/cadence) by increasing the amount of hip flexion and/or extension using power supplied by the device. Thus, the HWA applies continuous, step-by-step cueing to individuals with PD to take bigger and more symmetrical steps, thereby producing a faster and more efficient walking pattern. By wearing the HWA device over an extended period of time, individuals with PD will repetitively practice walking with a more “normal” gait pattern, possibly driving neuroplastic changes that will translate to improve unassisted walking. *We hypothesize that an 8-week intervention of HWA device usage will improve gait efficiency, gait parameters, perceived ease of walking, self-confidence, and daily physical activity in the home and community in individuals with PD with and without the use of the device.* Positive findings would justify larger clinical trials to determine the efficacy of HWA device usage to encourage adherence to rehabilitation programs and to promote maintenance of an active lifestyle in individuals with PD.

METHODS

Participants: Adults aged 50-80 (n=46) who ambulate without assistance (Hoehn & Yahr stages 1-3) with diagnosed idiopathic PD and on stable doses of Parkinson’s medications for at least 4 weeks prior to the study will be recruited from the Ohio State Movement Disorders Clinic and community support groups. Exclusion criteria will be: presence of other significant cardiac, neurological or orthopedic problems that affect gait, weight more than 220 pounds and height greater than 6’8”, electronic medical devices embedded in the body, participating in any physical therapy, and inability to understand instructions

required by the study. **Study Design:** Proof-of-concept of the HWA device has already been established in prior single arm studies.¹⁴⁻¹⁸ This study will be a prospective Phase II randomized controlled trial to assess preliminary efficacy. **HWA Device:** The HWA device weighs 5.95 lbs and has two motors that run on a single rechargeable battery (Figure 2). The device is equipped with angle and current sensors to monitor hip joint angle and torque output respectively. The assist torque is transmitted to the user's thighs via thigh frames. A trained healthcare

professional, who operates the device, can remotely change assist settings through software that runs on a mobile device. Honda will provide the researchers with a minimum of 3 HWA devices of different sizes for use in this study. The HWA devices have points of adjustability at the Waist Frame and Thigh Frames (Figure 2), such that the devices can accommodate ~75% of adult, United States (US) body sizes. **Randomization:** After obtaining written informed consent, participants will be randomly assigned to 1 of 2 groups (Trained – HWA group, Untrained – usual care group). Randomization allocation will be 1:1 and stratified by Hoehn & Yahr stage. Each stratum randomization scheme will be generated in permuted blocks of varying size. These techniques will help to ensure a balance in the randomization among stage. The randomization scheme will be prepared, uploaded and overseen by the study's biostatisticians. Given the nature of the intervention proposed, participants will know the intervention to which they have been assigned. Therefore, it will only be possible to blind assessors in this study.

Procedures: Demographic information will be collected (i.e., age, sex, disease duration, Parkinson's medications, numbers of falls in past 6 months) and a neurologist with UPDRS motor rating certification will administer the Unified Parkinson Disease Rating Scale (UPDRS) Part III –Motor Scale²³ to assess motor impairments and determine the Hoehn and Yahr stage. A researcher who is blinded to the participants' group allocation and trained on relevant assessments will perform all outcome assessments. Assessments will be collected with participants in the ON phase at around one hour after taking their usual Parkinson's medications. *The primary outcome measure, gait velocity, will be used to validate the effectiveness of the HWA to improve gait parameters for both Aim 1 and 2.* Gait velocity (e.g., walking speed) correlates with functional ability and has been linked to clinically meaningful changes in quality of life and in home and community walking behavior.²⁴ **Aim 1:** Only participants randomized to the Trained group (n=23) will complete this part of the study to eliminate exposure of the Untrained group to the HWA device. Gait assessments will be conducted first during unassisted walking followed by HWA-assisted (i.e., wearing the HWA device) walking, with rest breaks allowed between tests. Prior to HWA-assisted walking, the researcher will select the appropriate sized HWA device, assist the participants to correctly don the device, and adjust the HWA device settings to maximize the participants' safety while walking. The PIs are experts in application and use of the HWA device (preliminary data and unshown pilot studies). Initial device settings will be symmetrical flexion and extension assist bilaterally. The research therapist will make adjustments as needed based on the response to the symmetrical assist setting. If the therapist is unable to adjust the HWA to provide a safe gait pattern the testing will be ended and the device removed. Safe gait is defined as one that results in no increase in incidence of

[figure not shown]

Figure 2. Components of the HWA Device

stumbles and/or balance loss during HWA-assisted walking as compared to unassisted walking.

Outcomes: Gait efficiency will be assessed with the six-minute walk test (6MWT),²⁵ gait parameters (i.e., velocity, stride length, swing time, double support, and their coefficients of variability) using GAITRite,²⁶ gait safety using counts of observed episodes of stumbles and/or loss of balance, and participants' perceived ease of walking as indicated on a visual analog scale (100 mm line with anchors "Not at all easy" on the left end and "Extremely easy" on the right end). The GAITRite System[®] (CIR systems, Inc.: Havertown PA) is a 4.88 m electronic walkway with sensors arranged in a gridlike pattern to capture footfall contacts. The application software (version 3.9) processes the raw data into footfall patterns and computes spatial and temporal parameters. Participants will walk at a normal, comfortable pace across the walkway for 4 trials. The first trial under each condition will be a practice trial and the data from the remaining three trials for each condition will be averaged. **Aim 2:** All individuals (n=46) will participate in this part of the study. **Intervention:** After undergoing the pre-assessment, participants randomized to the Trained group will be fitted with the HWA device in their home by a research physical therapist. They will be directed to walk with the device on and the therapist will adjust the settings until a safe gait pattern is obtained. The initial setting used will be the one that produced the safest walking at the pre-assessment. Adjustments will be made based on the response to this initial setting. Participants who achieve a safe gait pattern will receive physical therapist supervised home and community-based walking training wearing the HWA device 2 times per week for 45-60 minutes for 8 weeks. Training will consist of walking in and outside of the home while encouraging larger and more symmetrical steps with practice of activities (e.g., multi-directional stepping, turning, navigating around obstacles) that challenge the person's balance and motor control. Rest breaks will be allowed as needed. If the therapist is unable to adjust the HWA to provide a safe gait pattern, the session will be ended and the device removed. The Untrained group will continue their usual daily activities including any exercise regimen that they typically perform. However, they will be asked not to start any new exercise program during the study period.

Outcomes: All assessments will be performed within one week prior to and after the 8 week intervention in the researcher's laboratory at the Ohio State University with the exception of the activity monitors. The Untrained group will only perform gait assessments without use of the HWA. The same outcomes will be used from Aim 1 with addition of the Stanford Self-Efficacy for Measuring Chronic Disease 6-Item Scale (SSE)²⁷ questionnaire to measure participants' confidence in performing daily activities. The SSE has been found to have good reliability and validity in individuals with Parkinson's disease.²⁸ To determine changes in activity levels, all participants will wear activity monitors (e.g., Biosensics LEGSysTM and PAMSysTM system wearable accelerometers) to quantitatively measure physical activity (e.g., number of steps, time spent walking, gait parameters, number of falls) for 5 consecutive days and complete a diary recording their daily activities during weeks 1 and 8 of the intervention period. To monitor safety during the study period the participants will be asked to record any falls (i.e., an event which causes the person to rest inadvertently on the ground or floor) or other adverse events that occur in a diary. **Sample Size:** The primary outcome for Aim 1 is to compare gait velocity pre and post treatment. For Aim 1, we will use the 23 patients randomized to the treatment arm and will have at least 80% power to detect a difference of 0.61 standard deviations in gait velocity using a two-sided paired t-test with type I error rate of 0.05. The primary outcome for Aim 2 is the gait velocity at 8 weeks. For Aim 2, we will have at least 80% power with 18 evaluable patients per group to detect a difference of 0.96 standard deviations in gait velocity at week 8 using a two-sided t-test with type I error rate of 0.05. Assuming a loss to follow-up rate of 20%,

we will enroll 23 patients per group for Aim 2. **Data Analysis:** The primary outcome for Aim 1 is the change in gait velocity with and without the use of the HWA device. This analysis will compare the difference in gait velocity using a paired t-test. The test of the with/without HWA gait change will be two-sided and at the 0.05 level. Exploratory analyses may consider associations of difference with patient characteristics such as Hoehn & Yahr stage. Secondary outcomes for Aim 1 will be analyzed similarly using appropriate methods for paired data. The primary outcome for Aim 2 is gait velocity at 8 weeks. The primary analysis will follow intention to treat principles to preserve the balancing properties of randomization.^{29,30} The primary analysis will assess the effect of treatment on gait velocity at 8 weeks using a linear regression model that includes an indicator of treatment, stage, and baseline gait velocity. The test of the treatment effect will be two-sided and conducted at the 0.05 significance level. Sensitivity analyses will examine the per protocol population (those who followed the assigned treatment correctly) and will utilize methodology for handling missing data (i.e., multiple imputation) to account for loss to follow-up.

Exploratory analyses may explore differences in the treatment effect across baseline patient characteristics (such as Hoehn & Yahr stage). Secondary outcomes for Aim 2 will be assessed similarly to the primary outcome using appropriate generalized linear models. **Interim Monitoring** We will conduct an interim analysis to ensure that the rate of patients in the treatment arm unable to attain a safe gait is not unacceptably high. We will evaluate the failure rate after 10 patients in the treatment arm complete the study. If 5 or more of the 10 patients fail to attain a safe gait with the device, the study will stop to determine if termination is warranted. Assuming an acceptable failure rate is 20%, we would have a 62% chance of correctly stopping the study early with an observed failure rate of 0.5. With the same assumptions, we also have a 3% chance of incorrectly stopping the trial. According to Honda R&D personnel, all participants who have met inclusion criteria during studies with the device have been able to safely use the device during walking. Therefore, the failure rate of 20% is an estimation and not based on preliminary findings. We will also conduct an interim analysis of data to ensure data quality and refine data analysis processes at the end of 12 months.

[figure not shown]

Figure3. Study Flowsheet

References

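### No check that the device fits is described before randomisation, so people who cannot wear it could be allocated to the Trained arm and dilute the Aim 2 intention-to-treat effect

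*Combined protocol and SAP*

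**What the plan says.** All references are to the combined protocol and SAP, Methods.

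- **HWA Device.** The manufacturer supplies "a minimum of 3 HWA devices of different sizes for use in this study". They adjust at the waist and thigh frames, so that "the devices can accommodate ~75% of adult, United States (US) body sizes".
- **Participants.** The only body-size criterion is the exclusion "weight more than 220 pounds and height greater than 6’8" (feet and inches).
- **Randomization.** "After obtaining written informed consent, participants will be randomly assigned to 1 of 2 groups". No fit check is described before this step.
- **Procedures, Aim 1.** Only the Trained group does this part, "to eliminate exposure of the Untrained group to the HWA device". This is where sizing first appears: before assisted walking, "the researcher will select the appropriate sized HWA device".
- **Aim 2, Intervention.** The Trained group is fitted again at home, and only those who reach a safe gait in the device go on to training.
- **Sample Size and Data Analysis.** Aim 2 is sized at 18 evaluable per group, raised to 23 for 20% loss to follow-up. Its primary analysis is by intention to treat, using a regression adjusted for stage and baseline gait velocity. Per-protocol and multiple-imputation analyses are sensitivity analyses.

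The text does not say how a Trained participant who cannot be fitted is to be handled.

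**The concern.** Whether a device fits is a property of the person that can be established before allocation. The plan acknowledges that some adults fall outside the devices' range, but as written it would discover this only after randomisation and only in one arm.

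A Trained participant who cannot be fitted affects both aims. For Aim 1 there is no assisted walk, so the pair is lost. For Aim 2 there are two routes:

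- The person stays to week 8 and is analysed as Trained without having been trained, which pulls the arm difference towards zero.
- The person leaves and becomes missing for a reason that cannot arise in the Untrained arm. This uses up part of the 20% loss allowance on one side only.

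The sample size makes no separate provision for people who are followed but untreated.

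**Working it through.** **Inputs from the documents.** Aim 2: 0.96 SD, two-sided 0.05, two-sample t-test, 80% power, 18 evaluable and 23 enrolled per group. Aim 1: 0.61 SD, n = 23, paired t-test. Interim rule: stop and review if 5 or more of 10 Trained participants fail to attain a safe gait.

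**Assumptions, not in the documents.** Let f be the share of eligible Trained participants who cannot be fitted. They have zero treatment effect, and wearers have the full 0.96 SD. The plan gives 0.96 SD as a detectable difference, not as an expected effect in wearers, so this is an illustration.

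**Step 1: reproduce the plan.** With n per group, the noncentrality is d × √(n/2) on 2n − 2 degrees of freedom. For n = 18 and d = 0.96 it is 0.96 × 3 = 2.88 on 34 df, giving power 79.9%. Enrolment is 18 / 0.80 = 22.5, rounded up to 23. Aim 1 with n = 23 and 0.61 SD gives 79.8%. The plan's figures hold.

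**Step 2: dilution when those who cannot be fitted stay and are analysed.** The arm difference becomes 0.96 × (1 − f).

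| f | Expected among 23 Trained (23 × f) | Arm difference | Power, 18 per group | Power, all 23 per group |
|---|---|---|---|---|
| 0% | 0 | 0.96 SD | 79.9% | 88.9% |
| 5% | 1.2 | 0.91 SD | 75.7% | 85.6% |
| 10% | 2.3 | 0.86 SD | 71.2% | 81.7% |
| 25% (upper reference only) | 5.8 | 0.72 SD | 55.5% | 66.6% |

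**Step 3: effect of the planned baseline adjustment.** The correlation r between baseline and week-8 velocity is not given. If it is 0.5 to 0.7 (assumed), the standardised difference is divided by √(1 − r²). At 18 per group, power is then about 90% to 98% with no misfits, 87% to 96% at f = 5% and 83% to 94% at f = 10%. The level rises, but the effect estimate is still multiplied by 1 − f.

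**Step 4: when those who cannot be fitted leave.** The allowance is 23 − 18 = 5 per group. Two such departures from Trained would use two of the five before any ordinary loss, with nothing to match them in Untrained.

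**Step 5: Aim 1.** Losing assisted data lowers power from 79.8% (n = 23) to 77.9% (n = 22), 75.8% (n = 21) and 73.5% (n = 20).

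**Step 6: would the interim rule catch it?** The text does not say whether inability to fit counts as failing to attain a safe gait. If it does, the binomial chance of 5 or more in 10 from misfit alone is 0.2% at f = 10% and 7.8% at f = 25%.

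**The case against.** **The misfit rate may be low, even near zero.** This largely stands. The 75% describes all US adults, not patients who meet these criteria. The Interim Monitoring section reports the manufacturer's statement that everyone who met inclusion criteria in earlier device studies could walk safely with it. Whether those criteria covered fit is not stated, so the report points to the low end without closing the gap. A reader might infer from the 75% that a quarter of the Trained arm, about 6 of 23, will be unable to wear the device and that power will be 56%. The documents do not support that reading.

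**A size screen already exists.** The exclusion joins weight and height with 'and'. Taken literally, it removes only people over both limits, which would be almost nobody, so two separate limits were probably meant. It would be unfair to argue from the literal reading that large people get through. Even as two limits, however, it says nothing about small body sizes, or about the waist and thighs where the device adjusts.

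**The power figures are pessimistic.** This partly stands. The 18-per-group column spends the whole loss allowance and then adds dilution, and it ignores the baseline adjustment. The 23-per-group column and Step 3 show milder results. Neither removes the dilution.

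**Other provisions deal with non-users.** The interim rule and the two sensitivity analyses show that the plan expects some Trained participants not to manage the device, but none screens fit before allocation. A per-protocol analysis would drop those who cannot be fitted from one arm while their counterparts stay in the other.

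**Including non-users is legitimate, and feasibility is an objective.** Both are true, and the dilution does not inflate type I error. But the trial also sets out to assess preliminary efficacy, and screening logs can still record how many people the device does not fit.

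**A fit check may exist outside the text.** A reader might infer that the plan rules out pre-screening. It does not: the text is silent, and Figure 3 could not be checked.

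**Conclusion.** The gap is real. The text allows people who cannot wear the device to be randomised to it, and it gives no rule for them. The size is uncertain and probably modest. At 5% to 10% misfit (about 1 or 2 of 23), the unadjusted illustration loses about 4 to 9 percentage points of power at 18 per group (79.9% to 75.7% or 71.2%), and about 3 to 7 points if all 23 are analysed (88.9% to 85.6% or 81.7%). These figures assume no effect in people who cannot be fitted and 0.96 SD in wearers. Baseline adjustment would make the absolute figures better. The 25% row is an outer bound from the general adult population, not a forecast. The point does not put the validity of the test in doubt. It is worth acting on because the remedy is cheap and must be in place before allocation to work.

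**What to change.** 1. Add an eligibility criterion, checked in every candidate before randomisation, that waist and thigh dimensions lie within the manufacturer's stated adjustment range for the devices supplied to the site. The documents do not give this range, so it must be obtained from the manufacturer and written into the protocol. Use a tape measure, not a try-on, so that the Untrained group stays unexposed to the device.
2. Log the people excluded for fit at screening and report the count, so that the feasibility objective is still served.
3. Reword the weight and height exclusion so that it is clear whether these are separate limits.
4. State how a participant found after randomisation not to fit is handled in the Aim 1 analysis, the Aim 2 analysis and the interim count.

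The cost is a few lines of protocol text and a few minutes at screening. The recruitment pool becomes slightly smaller, tape measurements may misclassify borderline fits in either direction, and the results will apply to people whom the device fits.

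### The plan places open randomisation after consent with no baseline test before it, so the Aim 2 baseline velocity can be measured after participants know their arm

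*Combined protocol and SAP*

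**What the plan says.** All places are in the Methods of the combined protocol and SAP.

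- **Randomization, timing:** "After obtaining written informed consent, participants will be randomly assigned to 1 of 2 groups". This is the only statement of when assignment happens.
- **Randomization, stratification:** "Randomization allocation will be 1:1 and stratified by Hoehn & Yahr stage".
- **Randomization, blinding:** "participants will know the intervention to which they have been assigned", followed by "Therefore, it will only be possible to blind assessors in this study".
- **Procedures:** a neurologist gives the UPDRS motor examination "to assess motor impairments and determine the Hoehn and Yahr stage".
- **Procedures, Aim 1:** "Only participants randomized to the Trained group (n=23) will complete this part of the study to eliminate exposure of the Untrained group". Within that session, unassisted walking comes first and device-assisted walking second.
- **Aim 2, Intervention:** "After undergoing the pre-assessment, participants randomized to the Trained group will be fitted with the HWA device in their home". The starting device setting at home is the safest one found at the pre-assessment.
- **Aim 2, Outcomes:** the Untrained group is tested only without the device. Laboratory assessments fall in the week before and the week after the 8-week intervention. That window is tied to the intervention and not to randomisation.
- **Data Analysis, Aim 2:** the primary analysis is a "linear regression model that includes an indicator of treatment, stage, and baseline gait velocity".

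**The concern.** Adjusting for a baseline value is safe when allocation cannot have influenced it. Here the covariate is walking speed at a pace the participant chooses, and participants are not blinded. Someone who knows that robot training is coming, or who is disappointed to be a control, may walk at a different pace on the walkway. The six-minute walk depends on effort, and the ease-of-walking scale and self-efficacy questionnaire are self-rated, so they are open to the same influence. A blinded assessor does not remove a change in the participant's own behaviour, and neither does analysis by intention to treat.

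At stake is the Aim 2 treatment effect. A difference in baseline created by knowing the arm would be treated by the model as a chance imbalance and corrected for, which moves the estimate. Secondary outcomes analysed with similar models are exposed in the same way.

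**Working it through.** **1. The order of events**

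- Consent comes before assignment; this is stated.
- Assignment comes before the device-assisted part of the pre-assessment. This follows because only the Trained group does that part, and its result sets the starting point for home training.
- Staging should come before assignment, because stage is the stratification factor, unless a stage already on record is used.
- The unassisted baseline tests have no stated position relative to assignment or disclosure. The natural reading is consent, assignment, pre-assessment, home fitting. Because unassisted walking opens the session, assignment or disclosure between the two walking blocks would also fit the wording.
- The activity-monitor recording is not in doubt: its first period is week 1 of the intervention, so it follows assignment.

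**2. The plan's own figure**

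Inputs from Sample Size: 18 evaluable per group, difference 0.96 SD, two-sided t-test at 0.05. The noncentral t gives power 0.799, which matches the stated 80%. Enrolment is 18 / (1 − 0.20) = 22.5, rounded up to 23 per group, also as stated. Nothing here disputes these figures.

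**3. Bias from a shifted baseline**

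Assumptions not in the documents: r is the baseline to week-8 correlation; knowing the arm lowers Trained baseline velocity by b SD relative to Untrained; a fraction p of that shift remains at week 8; there is no true effect.

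Adjusted effect = (week-8 difference) − r × (baseline difference) = −p·b − r·(−b) = b(r − p).

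Standard error ≈ √[(2/18)(1 − r²)]. Degrees of freedom are 36 − 4 = 32 (intercept, treatment, stage as one term, baseline), so the critical value is 2.037. The two-sided rejection rate comes from the noncentral t with noncentrality bias/SE.

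With b = 0.2:

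| r | SE | Bias, p = 0 | Type I error, p = 0 | Bias, p = 1 | Type I error, p = 1 |
|---|---|---|---|---|---|
| 0.5 | 0.289 | 0.10 | 6.3% | −0.10 | 6.3% |
| 0.7 | 0.238 | 0.14 | 8.8% | −0.06 | 5.7% |
| 0.9 | 0.145 | 0.18 | 22.5% | −0.02 | 5.2% |

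Example at r = 0.7, p = 0: bias 0.7 × 0.2 = 0.14; SE = √(0.1111 × 0.51) = 0.238; noncentrality 0.14/0.238 = 0.59; rejection rate 8.8%. Simulation of the planned regression, without the stage term, gave rates close to the p = 0 column (about 22% at r = 0.9).

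Other values:
- Half persistence (p = 0.5, b = 0.2): 5.3% at r = 0.7 and 8.3% at r = 0.9.
- Smaller shift (b = 0.1, p = 0): 5.3% to 9.2% over r = 0.5 to 0.9.
- Larger shift (b = 0.3, p = 0): 8.0% to 43.8% over the same range.

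If Trained participants walk faster at baseline, every sign reverses and the rejection rates stay the same. Against the 0.96 SD target, a bias of 0.10 to 0.18 SD is 10% to 19% (0.10/0.96 and 0.18/0.96).

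**The case against.** The strongest reply is that the order is inferred. A reader might conclude that participants are randomised straight after consent and that baseline velocity is measured with the arm known. The documents do not support either as fact. They say after consent, not immediately after, and stratification by stage implies an examination in between unless a prior stage is used. Staging is described later in the text than randomisation but is needed before it, so the order of paragraphs is a poor guide to the order of events. Participants will know their arm, but when they are told is not given. Figure 3, the flowsheet, might settle the matter; it is not available here, and its absence cannot be held against the plan. All of this stands.

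The second reply concerns size. A reader might take 9% to 22% as the trial's true type I error. Those figures need a 0.2 SD shift, a correlation of 0.7 to 0.9, and a shift that disappears by week 8 even though participants still know their arm. With full persistence the error is 5% to 6%. Neither the size nor the direction of any shift is documented. This stands too: bias is possible, not shown.

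Third, some participants may withdraw on learning their arm and leave no baseline, but that is conjecture, and no weight is put on it here.

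The core remains. The one sequence the text states puts assignment after consent and no baseline test before it, participants are unblinded, and the exposed measurement is the covariate in the primary model.

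**Conclusion.** The point holds as avoidable exposure to bias. Followed as written, the plan allows the Aim 2 baseline velocity, and the six-minute walk, ease-of-walking and self-efficacy baselines, to be collected after participants know their arm. It does not establish that they will be, or that any bias will follow.

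The size depends on three unknowns: the shift, the correlation and the persistence. For a 0.2 SD shift that does not persist, bias is 0.10 to 0.18 SD and type I error roughly 6% to 22% for correlations of 0.5 to 0.9. With full persistence, type I error is close to nominal at about 5% to 6%.

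The change is worth making because it replaces the stated sequence with a safer one at little cost. It protects the baseline only: week-8 walking and self-ratings remain open to knowledge of the arm whatever the order.

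**What to change.** Amend the Randomization paragraph, for example: *Once written consent has been given, Hoehn & Yahr staging and all unassisted baseline tests (walkway, six-minute walk, ease-of-walking scale, self-efficacy scale) will be completed and recorded before assignment is generated or disclosed. Device-assisted Aim 1 testing will then follow in the Trained group only.* Make the flowsheet agree with this order.

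The plan already puts unassisted walking first, so no new test is needed, and the 18 evaluable and 23 enrolled per group and the power are unchanged. The cost is that the allocation must be available between the unassisted and assisted tests. The documents do not say whether consent, staging and laboratory testing share a visit; if they do not, a short scheduling change is needed. The activity-monitor recording in week 1 is not affected by this change; a pre-assignment recording would need its own schedule change.
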